### 4 **Rationale**

#### 4.1 **Rationale for study design**

Until now long-term safety and tolerability data of erenumab in a large group of patients are still limited. This 128-week open-label study will provide further treatment to patients still blinded for the randomization of the study CAMG334ADE01 (Eudract number:2019 -

Novartis	Confidential	Page 19
Clinical trial protocol V01	Protocol No. CAMG334ADE03	-

002201 - 22) and will provide data about the long-term safety and tolerability of Erenumab and patients' quality of life during long-term treatment. The regular assessments in a controlled trial allows a close observation of safety parameters during long-term treatment with erenumab. Furthermore, while regular reviews of treatment outcome and drug holidays are routine in migraine prophylaxis and also recommended in the German S1 guideline (DGN 2018), there are no data regarding erenumab treatment yet. Besides options to adjust the dose, an optional drug holiday is therefore included in this open-label study and the effects of a treatment interruption on safety, tolerability, efficacy and quality of life will be investigated.

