#### 4.3 **Risks and benefits**

Erenumab was developed for migraine prophylaxis in a large clinical development program including more than 3.000 patients and has shown efficacy across the migraine spectrum. Key risks and benefits are briefly summarized below. For further information, please refer to the SmPC.

There were no significant findings in the toxicology studies with erenumab that would predict a risk to human patients. There were no significant effects on electrocardiogram (ECG) parameters, blood pressure or respiration rate in the single dose cardiovascular study in cynomolgus monkeys.

As of June 2018, the safety of erenumab in migraine prophylaxis was assessed from integrated safety analyses of 2537 migraine patients exposed to at least one dose of erenumab, with a cumulative exposure of 2310.3 subject-years (SY). Overall, the safety and tolerability profile of erenumab was similar between the 140 mg and 70 mg doses and comparable to placebo. Adverse drug reactions include injection site reactions, constipation, muscle spasms, and pruritus. The majority were mild or moderate in severity and rarely led to treatment discontinuation. To date, no important risk has been identified for erenumab.

Overall, to date, there is no evidence from non-clinical and clinical data of risk of cardiovascular effects. On the theoretical basis of the mechanism of action of erenumab, CGRP receptor blockade might reduce compensatory vasodilation, particularly under ischemic conditions. Therefore, cardiovascular effects continue to be monitored.

All biologicals, including fully human proteins, have the potential to induce immunogenicity leading to the development of specific anti-drug antibodies. So far, the development of antierenumab antibodies has only been observed with low incidence and was not associated with specific adverse events or a clinically relevant reduction in erenumab plasma levels. In most cases, subjects with a positive anti-erenumab antibody status reverted to antibody negative with continued follow-up. Subjects in clinical studies will continue to be monitored for the development of anti-erenumab antibodies and possible associated clinical sequelae.

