## 8 Visit schedule and assessments

The Assessment Schedule (Table 8-1) lists all assessments and when they are performed. All data obtained from these assessments must be supported in the subject's source documentation.

Subjects should be seen for all visits/assessments as outlined in the assessment schedule (Table 8-1) or as close to the designated day/time as possible. Missed or rescheduled visits should not lead to automatic discontinuation. Subjects who prematurely discontinue the study for any reason should be scheduled for a visit as soon as possible, at which time all of the assessments listed for the final visit will be performed. At this final visit, all dispensed investigational product should be reconciled, and the adverse event and concomitant medications recorded on the CRF.

In table 8-1 all assessments are shown and "X" indicate when the visits are performed.

During visits 101 to visit 199, intervals between visits should not exceed  $84 \pm 7$  days. If the visit has to be scheduled outside this window, an approval from the sponsor has to be collected to ensure patient safety.

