#### Confidential Protocol No. CAMG334ADE03

#### Table 8-1Assessment Schedule

	Screen															Follow up 
Visit number 	0	Baseline	V101	V102	V103	V104	V105	V106	V107	V108	V109	V110	V199	V201 – V20X	V101B	V301
End of week	-2 to 0	0	12	24	36	48	60	72	84	96	108	120	128	Every 12 weeks	NA	132
Obtain informed consent	х															
Demography	Х															
Medical history & prior medication 	х															
Complete Physical Exam	S												S		S	
Brief Physical Exam		S	S	S	S	S	S	S	S	S	S	S		S		S
Height	Х															
Weight	Х												Х		Х	
Vital Signs 	Х	Х	Х	Х	Х	Х	Х	Х	Х	Х	Х	Х	Х	Х	Х	Х
ECG	Х														Х	
Concomitant Medications		x	x	x	x	x	х	х	х	x	х	х	х	х	x	

Page 31

	Screen		During drug holiday	First visit after drug holiday	Follow up 											
Visit number 	0	Baseline	V101	V102	V103	V104	V105	V106	V107	V108	V109	V110	V199	V201 – V20X	V101B	V301
End of week	-2 to 0	0	12	24	36	48	60	72	84	96	108	120	128	Every 12 weeks	NA	132
Adverse Events 	Х	х	х	х	х	х	х	х	Х	х	х	х	Х	Х	х	х
Serious Adverse Events⁵	х	x	x	х	х	х	х	х	х	х	х	х	Х	х	x	х
Study Drug dispensing 		х	х	х	Х	Х	Х	х	х	x	х	х			x	
Chemistry/Hematology 8	Х														x	x
Urine pregnancy 		х	x	x	х	х	х	х	х	х	х	х	Х			
Serum Pregnancy	х														x	x
		· 						· 			 	 				

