#### Confidential Protocol No. CAMG334ADE03

Novartis

Clinical trial protocol V01

Page 32

Novartis	Confidential	
Clinical trial protocol V01	Protocol No. CAMG334ADE03	

	Screen					Ope	n-label	Treatm	ent Epo	och				During drug holiday	First visit after drug holiday	Follow up 
Visit number 	0	Baseline	V101	V102	V103	V104	V105	V106	V107	V108	V109	V110	V199	V201 – V20X	V101B	V301
End of week	-2 to 0	0	12	24	36	48	60	72	84	96	108	120	128	Every 12 weeks	NA	132
Open-label Treatment Phase Completion form													х			
Follow-Up Phase Completion form																x

1 – All study visit target dates are to be calculated from the Day 1 visit date and all study procedures for a given visit should be completed on the same day.

2 – The Follow-Up Visit is required 8 weeks after last IMP injection (erenumab). The Follow-Up visit can be skipped if any other safety follow up visit occurred 4 weeks after last study visit. 3 – Including prior prophylactic medication.

4 – Includes blood pressure, pulse and temperature.

5 – SAEs will be collected after signing of the informed consent through the end of the Follow-Up Epoch end of study. Non-serious AEs will be collected starting at Baseline Visit through the end of the Follow-Up Epoch.

6 – Study drug erenumab will be dispensed to the patient at the center during the applicable study visit for home application. Last study drug application will be at week 124.

8 - Should be additionally performed at any visit if deemed necessary by the investigator due to AEs

9 Should be performed/registered by the investigator prior to dosing during DBTE.

X = Assessment to be recorded in the source documents and the clinical data base; S = Assessment to be recorded as source documentation only.

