#### 8.4 **Safety/Tolerability**

Safety assessments will include:

- Treatment discontinuations due to AEs
- Adverse events (Section 10.1)
- Physical examination
- Vital signs
- ECG
- Height/weight
- Laboratory evaluations
- Pregnancy testing (females of childbearing potential)

Safety assessments are specified below with the assessment schedule detailing when each assessment is to be performed.

For details on AE collection and reporting, refer to AE section.

Table 8-2	Assessments & Specifications
Assessment	Specification
Physical examination	A complete physical examination will include the examination of general appearance, skin, neck (including thyroid), eyes, ears, nose, throat, lungs, heart, abdomen, back, lymph nodes, extremities, as well as vascular and neurological examination. If indicated based on medical history and/or symptoms, rectal, external genitalia, breast, and pelvic exams will be performed. A brief physical exam will include the examination of general appearance and will be at all visits starting from baseline visit, except where a complete
	physical examination is required (see above). Information for all physical examinations must be included in the source documentation at the study site. Clinically relevant findings that are present at screening must be included in the Medical History part of the eCRF. Significant findings made after first administration of investigational drug, which meet the definition of an Adverse Event must be recorded on the Adverse Event section of the eCRF.

Assessmen	Specification
Vital signs	Vital signs include blood pressure, pulse and temperature measurements. After the patient has been sitting for approximately five minutes, with back supported and both feet placed on the floor, systolic and diastolic blood pressure will be measured three times using a validated device, with an appropriately sized cuff. The repeat sitting measurements should be made at approximately 1 – 2 minute intervals and the mean of the three measurements will be used. In case increased blood pressure is recorded (systolic/diastolic) measurements have to be repeated at the end of the study visit for validation. In case the cuff sizes available are not large enough for the patient's arm circumference, a sphygmomanometer with an appropriately sized cuff may be used. The method to take temperature should be consistent throughout the study.

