2.1.1.4 Safety endpoints

Safety summaries (tables, figures) include only data from the on-treatment period with the exception of baseline data which will also be summarized where appropriate (e.g. change from baseline summaries). In addition, a separate summary for death including on treatment and post treatment deaths will be provided. In particular, summary tables for adverse events (AEs) will summarize only on-treatment events, with a start date during the on-treatment period (treatment-emergent AEs).

Discontinuation of treatment due to AE during the Treatment Epoch

Discontinuation of treatment due to AE during the Treatment Epoch is determined by the flag on the Treatment Completion eCRF page. "Death" as a reason for treatment discontinuation will be also included in AEs leading to treatment discontinuation.

Treatment-Emergent Adverse Event (TEAE)

Treatment emergent adverse events are defined as AEs occurred on or after the first dose of study treatment. AEs registered prior and after the first dose of study treatment are considered as treatment emergent if they have increased severity based on preferred term any time after the first dose of study treatment.

In case of missing data on a day of AE start date, the AE is considered as treatment emergent if *date of first dose of study treatment* \leq *latest possible start date*

Please, see section 5.1.2 AE date imputation for "latest possible start date" definition.

Serious Adverse Event (SAE)

SAEs are determined by the flag on the Adverse Events eCRF page.

Treatment-Related Adverse Event

Treatment-emergent adverse event is defined as treatment-related, if investigator considered it as having a reasonable possibility to be related to study treatment, which is reflected in the eCRF with a corresponding flag.

Adverse Event leading to dose adjustment

Adverse event is defined as leading to dose adjustment if at least one of the following actions was taken with the study treatment due to AE:

- dose increased
- dose reduced
- drug interrupted
- drug withdrawn

Novartis	Confidential	Page 12 of 34
SAP v1.1		CAMG334ADE03

Duration of exposure to IMP

For all calculations of exposure, dose date refers to receiving dose > 0. The duration of exposure to IMP is computed as min (last IMP dose date + 27, EoS date) – first IMP dose date + 1 either including the time of drug holiday or excluding the time of drug holiday.

Subject Incidence

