2.8.4 Other safety data

2.8.4.1 12-lead ECG

For the numeric ECG measurements

• ECG Mean Heart Rate

- PR Interval
- QRS Duration
- QT Interval
- QTcF Interval
- RR Interval

summary statistics will be presented by visit. Descriptive summary statistics for the change from baseline will be calculated for patients with available ECG data at both time points.

All ECG data will be listed by subject and visit.

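### The only scheduled post-baseline ECG is at the end of a drug holiday, so the planned ECG summary cannot describe effects during dosing, yet returners' readings count as on-treatment

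*SAP*

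**What the plan says.** Protocol 8.4 lists the ECG among the safety assessments and leaves its timing to Table 8-1: "Safety assessments are specified below with the assessment schedule detailing when each assessment is to be performed". In that table the ECG row is marked at Screening and at V101B, headed "First visit after drug holiday", and nowhere else. A patient who stops early has a visit "at which time all of the assessments listed for the final visit will be performed". Protocol 8.4.2 adds two confirmatory tracings when an ECG raises a safety concern, and asks for a process to review clinically significant ECG findings over the whole study.

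On the analysis side, SAP 2.8.4.1 summarises six numeric ECG measurements by visit, including QTcF, and states: "Descriptive summary statistics for the change from baseline will be calculated for patients with available ECG data at both time points". SAP 2.1.1.4 sets the data that qualify: "Safety summaries (tables, figures) include only data from the on-treatment period", with baseline as the exception. The SAP runs the on-treatment period from first dose to 84 days after the last dose actually given (2.1.1.1); protocol 12.5.2 says 112 days. Neither definition removes the drug holiday, although the SAP subtracts it from time under treatment.

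On purpose, protocol 4.1 says that the design "allows a close observation of safety parameters during long-term treatment". Protocol 4.3, after describing a theoretical concern about CGRP receptor blockade under ischaemia, says: "Therefore, cardiovascular effects continue to be monitored".

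**The concern.** Safety is the primary objective, and the report will contain a table of ECG change from baseline built under on-treatment rules in a 128-week study. A reader will naturally take it as evidence about the ECG during long-term erenumab. If its scheduled post-baseline readings all come from visits at which dosing had been interrupted, and only from patients who chose a holiday and attended V101B, it is not that evidence. A null result would then offer reassurance that the data cannot give. It would also be silent on patients who stopped for an adverse event, who have no scheduled ECG when they leave.

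**Working it through.** The plan states no figure for this point, so there is none to reproduce. The check compares the schedule with the analysis rules.

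1. **Scheduled ECGs.** Table 8-1 has 16 visit columns: Screening, Baseline, V101 to V110, V199, V201–V20X, V101B and V301. Read by column position, the ECG row is marked in column 1 (Screening) and column 15 (V101B). The alignment can be trusted: read the same way, Weight falls at Screening, V199 and V101B, and Chemistry/Hematology at Screening, V101B and V301. Dosing-phase visits V101 to V199 number 10 + 1 = 11, and 0 of 11 carry an ECG. Section 8 does not say whether the final visit means V199 or V301, but neither has an ECG, so early stoppers gain none.

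2. **Is V101B before the restart?** Dispensing is marked at V101B and not at the holiday visits V201–V20X. Footnote 6 to the table says: "Study drug erenumab will be dispensed to the patient at the center during the applicable study visit for home application". SAP 2.1.1.2 refers to ECGs among office assessments taken ahead of dosing. Together these point to a reading before the first post-holiday dose. No sentence says so outright, and a restart from leftover home supply is not explicitly excluded.

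3. **Days since the last pre-holiday dose at V101B**, for a holiday of H weeks. The SAP starts the actual holiday period 28 days after the planned last dose, giving 28 + 7H days. Counting from the last dose itself gives 7H days.

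| H (weeks) | 28 + 7H | 7H |
|---|---|---|
| 4 | 56 | 28 |
| 8 | 84 | 56 |
| 12 | 112 | 84 |
| 16 | 140 | 112 |
| 24 | 196 | 168 |

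V101B is thus within 84 days of the last pre-holiday dose for holidays up to 8 weeks (first count) or 12 weeks (second count), and beyond it for longer ones.

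4. **Does the reading count as on-treatment?** A returner has, by the SAP definition, a documented dose after the holiday, so the on-treatment period ends at least 84 days after that dose and V101B lies inside it. Example with assumed dates: last pre-holiday dose at week 8 (day 57) and a 24-week holiday counted from 28 days later. V101B is on day 57 + 28 + 168 = 253, which is 196 days after that dose. With dosing resumed and a last dose at week 124 (day 869), the period runs to day 869 + 84 = 953, or 869 + 112 = 981 under the protocol. Day 253 is inside. If the same patient is never dosed again, the period ends on day 57 + 84 = 141 or 57 + 112 = 169, and the same reading is outside. One later dose decides.

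5. **Under which visit is it reported?** SAP 2.1.1.2 maps ECGs to study visits by the nearest study-day window. Taking the target for week w as day 1 + 7w (the window table is not in the available text), week 36 is day 253, the V103 target. In this example the V101B reading could be tabulated as V103, a dosing-phase visit.

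**The case against.** The strongest reply is that few ECGs are a legitimate choice for an approved drug. Protocol 4.3 reports no evidence of cardiovascular risk and does not promise serial tracings; 4.1 speaks of safety parameters generally. Blood pressure and pulse are taken at every visit, adverse events are asked about at each visit, and an ECG at screening and at restart fits a check before dosing begins or resumes. This stands. A reader might infer that the schedule breaks a commitment to ECG monitoring in 4.1 or 4.3; the wording is too general to support that. What remains is that these statements, and the study-long review of ECG findings in 8.4.2, sit beside a schedule that yields no ECG at a dosing-phase visit, and the documents do not say how the two fit.

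A reader might also infer that V101B readings are drug-free and should all leave the on-treatment summaries. The documents do not support that either. They give no minimum holiday length and no elimination figure, and after a short holiday the reading falls within the SAP's own 84-day allowance. Dosing interrupted is as far as the text goes.

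It can further be said that SAP 2.8.4.1 already summarises by visit, lists every ECG by patient and visit, and that V101B is a visit of its own. The listing helps, but the nearest-window rule can override the visit label in the summary, so the separation is not secured.

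Finally, SAP 2.3.2 refers to a baseline definition in 2.1.1 that is not in the available text, so the exact comparison behind the two time points cannot be settled. Whichever baseline applies, this study schedules no post-baseline ECG at a dosing-phase visit.

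**Conclusion.** The point holds for scheduled readings. Scheduled ECGs at dosing-phase visits: 0 of 11. Scheduled post-baseline ECGs: none for a patient without a holiday, one for a patient who attends V101B. The change-from-baseline summary therefore cannot describe ECG effects during long-term dosing, and its main input would be counted as on-treatment for every returner who attends V101B.

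That V101B reflects interrupted dosing rests on the inference in step 2 of the working. That a returner's reading counts as on-treatment does not, since it lies between the first and the last dose or within the days allowed after the last dose. Unscheduled ECGs may be taken during dosing, but they would be prompted by events and would not form a systematic comparison. The documents give no figure for holiday uptake, so no count of contributing patients is offered.

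The consequence is confined to the descriptive ECG output; neither the primary nor the secondary endpoints depend on it. A reader might infer that an ECG visit must be added. The documents support only that the passages need reconciling, and this point prescribes no procedure.

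**What to change.** In SAP 2.8.4.1:

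- Tabulate V101B ECGs on their own, under a label such as 'end of drug holiday, dosing interrupted', with days since the last pre-holiday dose.
- Exempt V101B from the nearest-window mapping in 2.1.1.2, so that it cannot appear under a dosing-phase visit.
- Do not present as on-treatment any V101B reading that lies beyond the SAP's post-dose window counted from the last pre-holiday dose. That window is 84 days in the SAP and 112 in the protocol, so state which one applies.
- Compare the V101B date with the recorded date of first dose after the holiday and flag any reading taken after the restart. This tests the one inference on which the label depends.
- State that the schedule supports no conclusion about ECG changes during dosing.

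Separately, the sponsor should reconcile Table 8-1 with protocol 8.4.2 and with the monitoring statements in 4.1 and 4.3.

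The SAP changes use dates and readings already collected. They cost a few lines of text and some programming, and no patient procedure.

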2.8.4.2 Vital signs

Assessed vital signs include:

- Systolic blood pressure
- Diastolic blood pressure
- Pulse rate
- Temperature

Patient's values on blood pressure will be calculated as a mean of three readings. Readings with missing values will be ignored.

Descriptive summary statistics presented by type of measurement will contain vital signs measurements for each study visit as well as change from baseline.

All vital signs data will be listed by subject and visit.

2.9 Pharmacokinetic endpoints

Not applicable

2.10 PD and PK/PD analyses

Not applicable

2.12 Biomarkers

Not applicable

3 Sample size calculation

In general, the 750 subjects randomized for clinical trial CAMG334ADE01 will be eligible for participation in the open-label study. It is estimated that approximately 75% to 85% of the study population meaning 563~638 subjects will enroll in the open-label study thus allowing the collection of long-term safety, efficacy and quality of life data of a large group of patients.

In the three-year open-label phase II study 20120178 the proportion of patients reporting at least one AE was 87%. Based on this finding event rates and precisions were calculated for the proposed 128-week trial for the primary endpoint. In conclusion a study population of at least 500 patients was found to be sufficient for the primary endpoint with an adequate range in precision.

The calculation of effect size and precision for the secondary endpoints is based on the proportion of study discontinuation rates in the three-year open-label phase II study 2012017. 4.2% of 383 patients discontinued this trial due to adverse events. Effect size and precision for the proposed study with at least 500 patients were calculated. In conclusion a study population of at least 500 patients was found to be sufficient for the secondary endpoints with an adequate range in precision.

Novartis	Confidential	Page 22 of 34
SAP v1.1		CAMG334ADE03

4 Change to protocol specified analyses

Contrary to what was stated in the protocol, an interim analysis will be conducted. For details please refer to section 2.14 Interim analysis.

5 Appendix

